- Patient Assessment of BM-related Symptom Change on a 7-point ordinal scale

Study Visit Assessments:

- The following information will be captured in the eDiary at the Pretreatment Visit:
 - Pain Catastrophizing Scale
- The following information will be captured in the eDiary at the Randomization Visit before the first dose of study drug and at all subsequent study visits:
 - Short Form-12 Health Survey version 2 (SF-12v2)
 - EuroQol-5 Dimension (EQ-5D-3L)
 - Irritable Bowel Syndrome-Symptom Severity Scale (IBS-SSS)

Protocol-permitted OTC Medication for Diarrhea

- Throughout the study (Screening Period through Posttreatment Period), patients will be allowed to use loperamide (Imodium[®]) to assist in the management of their diarrhea. Loperamide will be provided to the patient at study visits to use as needed (at the patient's discretion) to stabilize their diarrhea throughout the study. Beginning at the Pretreatment Visit (when the patients receive the eDiary) through the Week 12/EOT Visit, the day (yesterday/today) and dose will be entered by the patient for each use of loperamide for diarrhea on an event-driven basis.
- Prescription medications for the treatment of diarrhea or IBS are not permitted during the study, from 4 weeks (28 days) before the Pretreatment Visit (or 3 months before the Pretreatment Visit for rifaximin) through the EOS Follow-up Phone Call (see [Appendix 2](#)).

Number of Patients:

Approximately 368 IBS-D patients (approximately 92 patients per treatment group) will be randomized into the Treatment Period.

Diagnosis and Main Criteria for Inclusion:

Inclusion Criteria

To be eligible to participate in the study, patients must meet all of the following criteria:

1. Patient has given consent by signing an ICF.
2. Patient is an ambulatory male or female aged 18 years or older at the Screening Visit.
3. Female patients are not pregnant and lactating females must agree not to breastfeed.
4. Female patients of childbearing potential (ie, women who are not postmenopausal or who have not had a bilateral oophorectomy, hysterectomy, or tubal ligation) who are sexually active with a male partner must agree to use one of the following methods of birth control from the date they sign the ICF until the End of Study Visit:
 - a. Hormonal contraception (ie, oral contraceptive, contraceptive implant, or injectable hormonal contraceptive)
 - b. Double-barrier birth control (eg, condom plus intrauterine device, diaphragm plus spermicide)

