7.7 CONCOMITANT MEDICINES

A complete list of drugs that are conditionally allowed and drugs that are not allowed as concomitant medicines for either episodic or chronic use is provided in [Appendix 2](#). Throughout the study (Screening Period through Posttreatment Period), patients will be allowed to use loperamide to assist in managing their diarrhea. Loperamide 2-mg caplets will be provided to the patient at study visits to use as needed (at the patient's discretion) to manage their diarrhea throughout the study. Patient dosing of loperamide should not exceed 16 mg/day (8 unit doses), consistent with the product label. Beginning at the Pretreatment Visit (when the patients receive the eDiary) through the Week 12/EOT Visit, the day and dose will be entered by the patient for each use of loperamide on an event-driven basis.

At the Screening Visit, all ongoing medicines or investigational products taken by the patient will be recorded. Past use of certain prescription medications (approved or unapproved) to manage IBS symptoms (including alosetron [Lotronex[®]], rifaximin [Xifaxan[®]], and eluxadoline [Viberzi[®]]), even if not ongoing at the time of the Screening Visit, will be recorded at the Screening Visit.

Prescription medications used to treat IBS-D may not be used during the 4 weeks (28 days) before the Pretreatment Visit (or during the 3 months before the Pretreatment Visit for rifaximin). OTC medications used to treat IBS-D, other than loperamide, may not be used during the study (from the time of the Screening Visit through the EOS Follow-up Phone Call). Other prohibited medicines may not be used during the Pretreatment, Treatment, and Posttreatment Periods, and may not be used during some or all of the Screening Period (refer to [Appendix 2](#)). Any changes in concomitant medicines or new medicines added after the Screening Visit will be recorded on the eCRF. Concomitant medicines will be recorded at study visits throughout the entire study. Use of loperamide for diarrhea will be documented by the patient via eDiary.

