- **Change from Baseline in Percent of Days with Use of Loperamide for Diarrhea at Each Week**
The percent of days using loperamide for diarrhea at each week will be calculated as 100 times the number of days loperamide was used during the week divided by 7.

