In addition to the patient assessment of stool consistency using the 5-point ordinal scale (described above), the stool consistency of each BM will be recorded by the patient by daily eDiary entry for each BM on an event-driven basis using the BSFS (Protocol Appendix 5), which depicts the stool consistency characteristics along with descriptions for each of them. The patient assigns a corresponding score for each BM. The BSFS is a well-accepted and widely-used measurement of stool consistency. The 7-point ordinal BSFS is provided below (see Protocol Appendix 5 for full scale including pictures):

“Please describe the form of your stool using the following scale where:”

- 1=Separate hard lumps like nuts (hard to pass)
- 2=Sausage-shaped but lumpy
- 3=Like a sausage but with cracks on the surface
- 4=Like a sausage or snake, smooth and soft
- 5=Soft blobs with clear-cut edges (passed easily)
- 6=Fluffy pieces with ragged edges, a mushy stool
- 7=Watery, no solid pieces, entirely liquid

BM Urgency

Patient assessment of BM urgency will be collected by eDiary entry on an event-driven basis (ie, for each BM reported in the eDiary). For each BM, urgency will be assessed by the patient using a binary scale:

“Did you feel the need to rush to the toilet in order to avoid an accident before your bowel movement?”

- 1=Yes
- 2=No

Use of Loperamide for Diarrhea

Patients will report use of loperamide (Imodium®) for diarrhea on an event-driven basis (ie, for each use of the medication). An evening report will ask whether the patient entered all loperamide use for that day and collect all loperamide use not previously entered for that day (recall is limited to the period of time following the patient’s completion of the previous night’s Evening Report [ie for an Evening Report completed yesterday at 10:00pm, no events can be recorded today with a time preceding 10:00pm yesterday], or time following 7:00pm the previous day in instances where the previous night’s Evening Report was missed by the patient).

“Did you use Imodium® (loperamide) for diarrhea that you have not yet reported in the Diary?”

- 1=Yes
- 2=No

“Was the Imodium[®] (loperamide) taken yesterday or today?”

1=Yesterday

2=Today

“How many Imodium[®] (loperamide) pills did you take?”

__ pill(s)

Weekly Patient Assessment of Bowel Movement-related Symptom Severity

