A 50% of days Daily Abdominal Pain 30% Responder is defined as a patient who achieves at least 30% decrease from baseline in daily abdominal pain score at its worst for at least 50% of days in the 12-week Treatment Period, which is at least 42 days. These 50% days with at least 30% decrease don’t have to be consecutive during treatment period.

- 50% of Days Daily Abdominal Pain 40% Responder

A 50% of days Daily Abdominal Pain 40% Responder is defined as a patient who achieves at least 40% decrease from baseline in daily abdominal pain score at its worst for at least 50% of days in the 12-week Treatment Period, which is at least 42 days. These 50% days with at least 40% decrease don’t have to be consecutive during the Treatment Period.

- 50% of Days Daily Abdominal Pain 50% Responder

A 50% of days Daily Abdominal Pain 50% Responder is defined as a patient who achieves at least 50% decrease from baseline in daily abdominal pain score at its worst for at least 50% of days in the 12-week Treatment Period, which is at least 42 days. These 50% days with at least 50% decrease don’t have to be consecutive during the Treatment Period.

Additionally, the cumulative distribution of patients satisfying 50% of days daily abdominal pain response based on the percent change from baseline will be plotted and tabulated by treatment group and by percent change from baseline in the daily abdominal pain at its worst.

Abdominal pain is measured daily using an 11-point NRS. Abdominal pain-free days will be those days where the patient reports a score of 0 for abdominal pain at its worst. The post baseline number of abdominal pain-free days per week will be calculated as the number of Abdominal Pain-free Days during the Treatment Period (from the first to the last dose), divided by the total number of days within Treatment Period times 7. The baseline percent number of abdominal pain-free days per week will be calculated as the number of Abdominal Pain-free Days during the Pretreatment Period (per defined Pretreatment Period), divided by the total number of days within the Pretreatment Period times 7. The descriptive statistics (n, mean, SD, median, minimum and maximum) for the baseline and post-baseline abdominal pain-free days

per week and the count of abdominal pain-free days during the Treatment Period will be tabulated by treatment group.

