- For each period of interest, the Percent of Days experiencing no episode of diarrhea will be 100% minus the percent of days experiencing episode of diarrhea.
- Change from Baseline in BM-related Symptom Severity through the Treatment Period
- Patient global impression of severity (PGI-S) of BM-related symptom severity on a 5-point scale will be reported weekly by eDiary entry. Weekly PGI-S will be summarized weekly and analyzed via MMRM.
- BM-related Symptom Change
- Patient global impression of change (PGI-C) of BM-related symptoms is measured weekly using a 7-point ordinal scale comparing the severity for the past 7 days to the severity before starting the study. The postbaseline weekly PGI-C score will be analyzed via MMRM (without baseline).

Urgent BM Frequency Rate and Number of Days with Use of Loperamide for Diarrhea per week will be defined similarly as Number of Abdominal Pain-free days per week and will be calculated as the total number of events within the entire Treatment Period (or Pretreatment Period for baseline) divided by the total number of days within the Treatment Period, then multiplied by 7. Similar to Number of Abdominal Pain-free Days per week, these endpoints will be summarized by treatment group and the relevant count data during the entire treatment period will be analyzed by Poisson regression for the comparison between any active treatment group and placebo. If the data is skewed to 0 (overdispersed), the Negative binomial model will be used.

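### The only loperamide endpoint counts days with any use, so a difference between arms in caplets per use-day is invisible to the planned loperamide analysis, although pill numbers are recorded

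*SAP*

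**What the plan says.** **Endpoint.** SAP 7.8.10 defines "Number of Days with Use of Loperamide for Diarrhea per week" by analogy with abdominal pain-free days, "calculated as the total number of events within the entire Treatment Period (or Pretreatment Period for baseline) divided by the total number of days", scaled to a week. The template in SAP 7.8.9.4 counts "those days where the patient reports a score of 0 for abdominal pain at its worst", so each day scores 0 or 1. The analysis is a Poisson regression on treatment and baseline with a treatment-duration offset, replaced by a negative binomial model if the counts are overdispersed. Protocol 10.4.5 also works in days: "100 times the number of days loperamide was used during the week divided by 7".

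**Data collected.** Protocol 7.7 states that "the day and dose will be entered by the patient for each use of loperamide on an event-driven basis", from the Pretreatment Visit to the Week 12/EOT Visit. The eDiary item in SAP 5.3.3 asks how many "pills did you take". Protocol 7.7 gives the caplet strength as 2 mg and a stated limit of 16 mg (8 unit doses) a day.

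**Other uses of the amount.** The investigator alert in protocol 8.2.6 is triggered by 8 or more unit doses in 24 hours on 5 or more consecutive days. It concerns single patients. The concomitant-medicine summary in SAP 7.8.7 counts a patient once per ATC category, without quantity. Neither document defines a treatment-group analysis or summary of pills or milligrams.

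**The concern.** The exploratory objective is to assess bowel-function changes with MD-7246. Loperamide is supplied to every patient, to be taken at the patient's discretion to stabilise diarrhea (protocol 5.2, SAP 3.2). Stool frequency, form, urgency and diarrhea episodes are therefore all recorded while patients adjust their own loperamide.

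Two situations can then look alike in the planned tables. In one, a dose leaves bowel function unchanged. In the other, it loosens stools and patients respond with more caplets on the same days, which brings the stool measures back towards placebo. Use-days are equal in both. The amount of loperamide is the recorded quantity that would separate them, and it is not analysed.

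This matters because protocol 3.2 expects little impact on bowel function, so a null result would agree with the product's premise and might be accepted without further question.

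**Working it through.** **1. The plan's own power figure.** The documents state power only for the Week 12 pain change, not for loperamide. With 92 per group, difference 1.0 and SD 2.4 (SAP section 4):

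- standard error = 2.4 × √(2/92) = 0.354
- 1.0 / 0.354 = 2.826, and 2.826 − 1.960 = 0.866
- power = Φ(0.866) = 0.807; the exact t calculation on 182 df gives 0.803

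The stated figure of about 80% is reproduced. Nothing below depends on it.

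**2. What the endpoint can register.** Inputs are 84 treatment days (SAP 7.8.9.4), 2-mg caplets and 1 to 8 caplets on a use-day (protocol 7.7). The 24 use-days are chosen for illustration.

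- Use-days per week = use-days / 84 × 7 = 24 / 84 × 7 = 2.0
- Caplets per week = use-days × caplets per use-day / 84 × 7

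| Caplets per use-day | Use-days per week | Caplets per week | mg per week |
|---|---|---|---|
| 1 | 2.0 | 2 | 4 |
| 2 | 2.0 | 4 | 8 |
| 4 | 2.0 | 8 | 16 |
| 8 | 2.0 | 16 | 32 |

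The endpoint does not move over an eightfold range of amount. This follows from the definition and needs no assumption about usage. The SAP's reference to events could be read as use entries rather than days, in which case two entries on one day would count twice. The pills within each entry would still be ignored.

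**3. Effect on a comparison between arms (illustration).** Assumptions not taken from the documents: the share of days with use follows a Beta(0.8, 2.4) distribution (mean 25%) in both arms, and one arm averages 1.5 caplets per use-day. With 92 per arm and 2,000 simulated trials, a t-test on log(1 + count) stood in for the planned count model.

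| Mean caplets per use-day in the other arm | Day count rejects | Caplet count rejects |
|---|---|---|
| 1.5 | 5.3% | 4.8% |
| 2 | 4.6% | 28% |
| 3 | 4.9% | 90% |
| 4 | 4.7% | 99% |

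The day-count column sits at chance by construction, because use-days were given the same distribution in both arms. That is the case at issue.

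**4. Sensitivity to the usage rate.** Other simulations used baseline adjustment, 92 per arm and about 2 caplets per use-day, with a 30% rise in pills per use-day. Power for the caplet measure was 44% and 61% at median daily use of 5% and 10%, with the day count at 4% and 5%. At median use of 20%, 35% and 50% it was 61%, 77% and 90%. Changing the assumed spread between patients gave about 82–99% over 20–50% use, 43% at 5% and 29% at 2%. Together with the 28% in step 3 (a rise of 33%, unadjusted), a rise of about 30% gives anything from 28% to 99%, depending on inputs the documents do not supply.

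**5. The opposite case.** If only the frequency of use changes (odds ratio 1.5, median use 20–50%), the day count had 86–91% power and the caplet measure 61–70%. Those runs used a linear model on days per week, not the SAP's Poisson or negative binomial model, so only the direction should be relied on.

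**The case against.** The strongest reply has four parts.

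- **Other endpoints cover bowel function.** Loperamide is one of eight exploratory bowel endpoints. Every bowel movement, its form and its urgency are logged, so loose stools that prompt extra caplets also enter the other seven. This stands in part. The loperamide endpoint does not carry the conclusion alone, and the SAP states no decision rule that rests on it. But the other seven are recorded under the same freely used loperamide, and one of them, days without a diarrhea episode, is only 100% minus another. They cannot fully replace the amount taken.
- **Heavy use is not expected.** SAP Appendix 1 justifies the count model by describing these events as relatively uncommon in IBS-D, and SAP 7.8.10 anticipates counts piled up at zero. This stands against giving weight to saturation: a patient who uses loperamide daily at baseline cannot exceed 7 days per week, but such patients are probably few. The loss of amount on the days that are used remains.
- **Frequency of use is a legitimate measure.** This stands, and step 5 shows it is the better one when only frequency changes.
- **The study is hypothesis generating and the endpoint is exploratory.** This stands and limits the importance of the point. The key pain endpoints are not directly affected.

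A reader might go further and infer that the plan would lead to a false conclusion of no bowel effect, or that a caplet analysis has a known power advantage. The documents support neither. They offer no evidence that caplets per use-day would rise with use-days unchanged, they provide several other bowel measures, and they give no usage rates from which to compute power.

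**Conclusion.** The point holds in a limited form. The planned loperamide analysis cannot see a difference between arms in caplets per use-day when use-days are unchanged: an eightfold range of amount gives the same value, and the test then rejects at about 5%. Such a difference could mask a bowel effect in the stool endpoints. That result rests only on the endpoint's definition and on the absence of any group analysis of pills. How often it would matter in this trial, and how much power a caplet analysis would have, cannot be settled from the documents, and the simulated percentages are illustrations. The use-day count should stay. The blind spot is confined to the planned tables, because the pill data exist. The addition is worth specifying before unblinding, since the amount taken bears on how the other bowel endpoints are read and choosing it afterwards would be post hoc.

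**What to change.** In SAP 7.8.10, keep the use-day endpoint and add beside it:

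- **Loperamide caplets per week:** total caplets recorded in the Treatment Period, divided by the days in that period, times 7. Take baseline from the 14-day Pretreatment Period in the same way. Analyse the total count by negative binomial regression with treatment, baseline caplets per week and a treatment-duration offset, and report each dose against placebo with a 95% CI. This stays within the SAP's own count framework and allows for unequal exposure. A linear model on log(1 + caplets per week) would fit a zero-heavy count poorly and would weight a short exposure the same as a full one.
- **Mean caplets per use-day by group:** total caplets divided by days with any use, as a descriptive summary only, because it is limited to patients who used loperamide after randomisation.

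State that both are to be read together with use-days and the other bowel endpoints when concluding on bowel function.

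The cost is a paragraph in the SAP and an exploratory table from data already collected. The downside is one more unadjusted exploratory comparison on a skewed variable. No dosing rule changes.

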7.8.1.1. Analysis Periods

For the purpose of analyses, three analysis periods are defined and will be used for different analyses.

The Pretreatment period is defined as the 14 days immediately prior to the date of the first dose of study drug.

The Treatment Period is defined as the period from the date of the first dose of study drug to the date of the last dose of study drug. This will be used as the primary efficacy analysis period unless otherwise specified.

The Treatment Emergent Period (TE Period) is defined as the period from the date of the first dose of study drug to 1 day after the date of the last dose. For analysis purposes, AEs and required medications will be considered treatment emergent if they occur within this period. TE period will be the primary analysis period for AEs and medications.

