A 9/12 Week Abdominal Pain Sustained Responder is a patient who meets the Weekly Abdominal Pain 30% Responder criteria for at least 9 out of the 12 weeks of the Treatment Period.
- 9/12 Week Abdominal Pain 50% Sustained Responder
A 9/12 Week Abdominal Pain Sustained Responder is a patient who meets the Weekly Abdominal Pain 50% Responder criteria for at least 9 out of the 12 weeks of the Treatment Period.
- 6/12 Week Abdominal Discomfort 30% Responder
A 6/12 Week Abdominal Discomfort 30% Responder is a patient who meets the Weekly Abdominal Discomfort 30% Responder criteria for at least 6 out of the 12 weeks of the Treatment Period.
- 6/12 Week Abdominal Bloating 30% Responder
A 6/12 Week Abdominal Bloating 30% Responder is a patient who meets the Weekly Abdominal Bloating 30% Responder criteria for at least 6 out of the 12 weeks of the Treatment Period.
- 6/12 Week Abdominal Cramping 30% Responder
A 6/12 Week Abdominal Cramping 30% Responder is a patient who meets the Weekly Abdominal Cramping 30% Responder criteria for at least 6 out of the 12 weeks of the Treatment Period.
- 6/12 Week Degree of Relief Responder
A 6/12 Week Degree of Relief Responder is a patient who scores ≤ 2 for at least 6 out of the 12 weeks of the Treatment Period.
- 6/12 Week Adequate Relief of IBS Pain Responder

A 6/12 Week Adequate Relief of IBS Pain Responder is a patient who reports adequate relief of IBS pain (“yes”) for at least 6 out of the 12 weeks of the Treatment Period.

The following responder endpoints are defined based on whether a patient satisfies certain criteria for the change from baseline in daily abdominal pain at its worst on at least 50% of protocol defined treatment days (84 days). If a patient did not enter information into the eDiary on at least 42 days during Treatment Period, the patient will not be considered a responder for any of the following responder endpoints. Numbers and percentages of patients satisfying these responder definitions will be summarized by treatment and the comparison between each active treatment group and placebo will be analyzed using a CMH test.

- 50% of Days Daily Abdominal Pain 30% Responder

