7.8.10. Exploratory Endpoints and Analyses

The following endpoints will be summarized and analyzed via a similar MMRM for the Change from Baseline in Abdominal Pain through the Treatment Period and at each week:

- Change from Baseline in BM Frequency Rate through the Treatment Period and at each week

For each period of interest (Pretreatment Period, Treatment Period, or a particular week), the BM frequency rate is a weekly rate, which is calculated as the total number of BM within the period divided by the total number of days during the period multiplied by 7. The change from baseline in BM frequency rate is the postbaseline frequency rate minus the baseline frequency rate. For weeks after the treatment discontinuation, this rate will be missing.

- Change from Baseline in BSFS (Stool Consistency) through the Treatment Period and at each week.

For each period of interest (Pretreatment Period, Treatment Period, or a particular week), the BSFS is the average of all available BSFS scores the period. The change from baseline in BSFS is the postbaseline BSFS score minus the baseline score. For weeks after the treatment discontinuation, this score will be missing.

- Change from Baseline in the Percent of Days Experiencing an Episode of Diarrhea through the Treatment Period and at each week

An episode of diarrhea is defined as a sequence of 2 or more loose/watery BMs (BSFS 6 or 7) that are never separated by >1 non-loose/watery stool or by a day without a BM. For each period of interest (Treatment Period, or a particular week), the percent of days experiencing an episode of diarrhea will be calculated as 100 times the number of days with a diarrhea episode divided by the total number of days with study treatment in the period. For baseline, the number of days with a diarrhea episode will be determined for the last 14 days of the Pretreatment Period. The baseline percent of days experiencing an episode of diarrhea will be calculated as 100 times the number of days experiencing an episode during the baseline period divided by the length in days of the baseline period (typically 14 days). The change from

- baseline will be calculated for each week as the weekly percent minus the baseline percent. For weeks after the treatment discontinuation, this percent will be missing.
- Change from Baseline in the Percent of Days Experiencing No Episodes of Diarrhea through the Treatment Period and at each week

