Appendix Table 3-1: Analysis Time Windows for Efficacy Analysis

Period	Analysis Week	Begins^a	Ends^a
Pretreatment (Baseline ^b)	Week -2	Day -14	Day -8
	Week -1	Day -7	Day 1 (time of first dose)
Treatment	Week 1	Day 1 (time of first dose)	Day 7
	Week 2	Day 8	Day 14
	Week 3	Day 15	Day 21
	Week 4	Day 22	Day 28
	Week 5	Day 29	Day 35
	Week 6	Day 36	Day 42
	Week 7	Day 43	Day 49
	Week 8	Day 50	Day 56
	Week 9	Day 57	Day 63
	Week 10	Day 64	Day 70
	Week 11	Day 71	Day 77
Week 12	Day 78	Day of last study treatment dose ^c (usually Day 85)	

Note: There is no Day 0 or Week 0. For eDiary assessments in which a patient is asked to report if an event occurred “yesterday” or “today” (e.g., a bowel movement), these windows pertain to when the event occurred, not to when the event is reported. For example, if a patient reports in eDiary on Day 78 a bowel movement occurring “yesterday,” that bowel movement (and subsequent stool consistency) would be included in Analysis Week 11, not Analysis Week 12.

- a Relative to the date of first dose; Day 1 = the day of first dose. For the calculation of rates in which the duration of a week or the overall period is calculated to the nearest hour, a day begins and ends at midnight.
- b Baseline values for efficacy parameters will be derived from the daily eDiary and eCRF data collected in the Pretreatment Period, specifically the period from 14 days before Randomization Visit up to the time of first dose.
- c For patients who fail to provide the date of last dose on the End of Treatment CRF form, the later date of the last known dose (drug dispense eCRF) or the last eDiary date will be used to impute the last dose date.

For the Treatment Period, diary day is calculated as diary date – date of first dose + 1. For the Pretreatment Period, diary day is calculated as diary date - date of first dose. However, the day of first dose is always trial Day 1.

If a patient withdraws during the Treatment Period, the patient’s Treatment Period shall end on the day of the last dose. The affected Treatment Period shall be shortened to the end of the withdrawn patient’s Treatment Period, and all subsequent weeks will be missing for that patient.

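### SAP 7.8.10 gives the baseline urgent-BM and loperamide rates a Treatment Period denominator, in conflict with the definition it cross-references; probably a drafting slip, but it needs correcting

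*SAP*

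**What the plan says.** SAP 7.8.10 covers two weekly rates, urgent BMs and days of loperamide use, and says that they "will be defined similarly as Number of Abdominal Pain-free days per week". The same sentence then gives its own formula, in which the event count is taken over the whole of treatment "(or Pretreatment Period for baseline) divided by the total number of days within the Treatment Period, then multiplied by 7".

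Other parts of the SAP that bear on it:

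- **7.8.9.4, pain-free days (the endpoint cross-referenced).** The baseline count is "divided by the total number of days within the Pretreatment Period times 7".
- **7.8.10, BM frequency rate.** For any period of interest the count is "divided by the total number of days during the period multiplied by 7", so numerator and denominator share a period. Baseline diarrhea days are likewise divided by the length of the baseline period.
- **7.8.1.1, period lengths.** "The Pretreatment period is defined as the 14 days immediately prior to the date of the first dose of study drug". For treatment, the section gives the "period from the date of the first dose of study drug to the date of the last dose of study drug". The notes to Appendix Table 3-1 add that for a withdrawn patient the "Treatment Period shall end on the day of the last dose".
- **7.8.9, general baseline rule.** It fixes the window for the baseline urgent-BM count but states no denominator, and it has no rule for loperamide.
- **Appendix 1.** It records the move of these endpoints from weekly MMRM to a count model, without a formula.

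**The concern.** A rate needs its events and its days from the same period. Here a count from a 14-day window is paired with the patient's days on drug, planned as 84. Two things follow if the formula is programmed as written. The baseline summary is on a different scale from the on-treatment rate tabulated with it. And a baseline quantity becomes a function of how long the patient stayed on drug, which is known only after randomization.

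Both endpoints serve the exploratory objective of assessing bowel function changes (SAP section 2), in a design that expects no significant effect on bowel function (SAP 3.2). A distorted baseline would obscure exactly that reading. There is also a practical risk: a programmer and an independent QC programmer could reasonably make different choices, one following the cross-reference and the other the formula.

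**Working it through.** **Inputs**

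- Baseline window: 14 days (SAP 7.8.1.1).
- Treatment Period length T: first to last dose, so it varies by patient (SAP 7.8.1.1). SAP 7.8.9.4 bases its day-based responders on "protocol defined treatment days (84 days)", and Appendix Table 3-1 gives Day 85 as the usual last-dose day.
- E: events in the 14-day baseline window. The SAP gives no expected value, so E = 14 (a true rate of 7 per week) is assumed for illustration. The ratios below do not depend on it.

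The SAP states no baseline rate, so there is no figure of its own to reproduce on this point.

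**Step 1. The two formulas**

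- Matching periods (as for pain-free days and BM frequency): E/14 × 7 = E/2.
- Literal 7.8.10: E/T × 7.
- Literal divided by matching: 14/T.

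**Step 2. Results for E = 14**

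| Days on drug, T | Matching rate per week | Literal rate per week (98/T) | Size of error |
|---|---|---|---|
| 85 | 7.0 | 1.15 | 6.07-fold too low |
| 84 | 7.0 | 1.17 | 6.0-fold too low |
| 42 | 7.0 | 2.33 | 3-fold too low |
| 28 | 7.0 | 3.5 | 2-fold too low |
| 14 | 7.0 | 7.0 | none |
| 7 | 7.0 | 14.0 | 2-fold too high |

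The last row shows that the literal formula cannot be what was meant for loperamide. A patient who used it on all 14 baseline days and stopped study drug after 7 days would have a baseline of 14 days of use per week.

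If the pre-dose part of Day 1 is counted as a 15th baseline day, the completer factor is 84/15 = 5.6 to 85/15 = 5.67 instead of about 6.

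**Step 3. Reach into the treatment comparison**

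SAP 7.2 says the baseline value enters Poisson models as a covariate. SAP 7.8.10 does not say in what form. The parallel model in 7.8.9.4 uses the baseline number of pain-free days, with an offset for treatment duration. A baseline count contains no T; the literal rate does.

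An illustrative simulation with no true treatment effect shows the size. Its assumptions, none taken from the documents except 92 per arm, were:

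- 15% dropout on placebo, with dropouts leaving between Day 7 and Day 79;
- gamma-distributed patient rates with a mean of 1 event per day;
- a negative binomial model with the baseline weekly rate as covariate;
- 200 replicates.

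| Extra dropout on active | Rate ratio, matching baseline | Rate ratio, literal baseline | Rate ratio, all baselines divided by 84 |
|---|---|---|---|
| 0 points | 0.993 | 0.996 | 0.993 |
| 15 points | 0.999 | 0.943 | 0.999 |
| 25 points | 1.002 | 0.913 | 1.002 |

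The last column shows that a constant six-fold rescaling does no harm to the comparison. The shift comes from the dependence on T, and only when T differs by arm.

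**The case against.** The strongest reply is that the sentence itself invokes the right rule. It says these endpoints are defined like pain-free days, and that definition divides the baseline count by Pretreatment days. The parenthesis was very likely meant to govern both halves of the fraction, and a programmer who followed the cross-reference would get the correct value. This stands as evidence of intent, and it is why the point is put as a probable slip and not as a chosen method. It does not remove the problem, because the general pointer is followed at once by an explicit formula that disagrees with it, and nothing else in the SAP says which prevails.

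A reader might also infer more than the documents support:

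- **That baseline is always understated six-fold.** This is so only for patients treated for about 84 days. The error shrinks with earlier withdrawal, is nil at 14 days and reverses below 14.
- **That every completer would seem to worsen.** With T = 84, the literal baseline is E/12 and the on-treatment rate is P/12, where P is events over 84 days. The patient seems worse only if P exceeds E. An unchanged patient has P = 6E and does seem worse; one whose true rate fell by more than 5/6 (about 83%) does not, and one with no events in either period shows no change.
- **That a false change from baseline would be reported.** The SAP specifies no change-from-baseline output for these two endpoints. It plans descriptive summaries and a model of the treatment-period count.
- **That the dose-placebo comparison is biased.** This needs the literal rate as covariate and discontinuation that differs by arm. The SAP does not specify the first, and the documents give no basis for assuming the second.

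Finally, both endpoints are exploratory and described as non-efficacy. The key endpoints are untouched.

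**Conclusion.** The formula in SAP 7.8.10 is wrong as written for baseline and contradicts the SAP's own parallel definitions. Taken literally, it multiplies the correct baseline weekly rate by 14/T: one sixth at 84 days, one half at 28, unity at 14, and above unity for shorter exposure. This rests on the 14-day analysis Pretreatment Period and the first-to-last-dose Treatment Period.

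The sure consequence of literal programming is confined to the baseline summaries of two exploratory endpoints, which would not be comparable with the on-treatment rates and would depend on post-randomization time on drug. An effect on the treatment comparison is conditional. Under the assumptions shown, the rate ratio moved to about 0.94 or 0.91 with 15 or 25 points more dropout on active drug, and stayed near 1.00 with equal dropout. If the baseline count is the covariate, the literal denominator does not enter the model at all. The correction is worth making before programming because the text supports two different programs.

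**What to change.** Rewrite the sentence in SAP 7.8.10 so that, for each of the two endpoints, events in a period are divided by the number of days in that same period and multiplied by 7: Pretreatment Period days for baseline, Treatment Period days for post-baseline. This matches the pain-free-days and BM frequency definitions.

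Add that any baseline covariate in the Poisson or negative binomial model uses pretreatment data only, and name which form is used: the Pretreatment count, or the weekly rate as just defined.

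The cost is a sentence or two in the SAP. No data collection changes, and the analysis that the cross-reference points to is unchanged.
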